10.5.1 Pfizer Expedited Reporting Guidelines

- Even though there may not be an associated SAE, exposure to the Pfizer Product during pregnancy and exposure to the Pfizer Product during lactation are reportable.
- The SAEs that are subject to this reporting provision are those that occur from after the first dose of the Pfizer Product through 28 calendar days after the last administration of the Pfizer Product or longer if so specified in the Protocol. In addition, investigators should submit SAEs to Pfizer any time after the administration of the last dose of the Pfizer Product, if the Investigator suspects a causal relationship between the Pfizer Product and the SAE.
- Investigators will assist Pfizer in investigating any SAE and will provide any follow-up information reasonably requested by Pfizer.
- The NF Operations Center will forward any SAE report within 24 hours (or immediately if the event is fatal or life-threatening) of learning of the event to Pfizer followed by a complete written report within 24 hours of the initial 24-hour report.

10.6 Reporting of Protocol Violations/Deviations and Unanticipated Problems

Site reporting to NF Operations Center

Sites will report unanticipated problems and/or protocol deviations that impact subject safety or the scientific integrity of the study to the Operations Center promptly at [contact]. Other protocol violations and deviations should be reported to the NF Operations Center annually.

NF Operations Center reporting requirements

The Operations Center will report unanticipated problems that impact subject safety or the scientific integrity of the study to the USAMRMC ORP HRPO promptly. Unanticipated problems will also be reported to the protocol team, Medical Monitor, and DSMB.

All unanticipated problems involving risk to subjects or others must be promptly reported by the NF Operations Center via [contact]), email ([contact]), or [contact]) to the HRPO. A complete written report will follow the initial notification. In addition to the methods above, the complete report can be sent to the US Army Medical Research and Materiel Command, ATTN: MCMR-RP, [name].

Suspensions, clinical holds (voluntary or involuntary), or terminations of this research by the IRB, the institution, the Sponsor, or regulatory agencies will be promptly reported to the USAMRMC ORP HRPO.

Other protocol violations and deviations that do not impact subject safety or affect scientific integrity of the study will be provided annually to the Sponsor.

11.0 CRITERIA FOR REMOVAL FROM PROTOCOL THERAPY AND OFF STUDY CRITERIA

11.1 Criteria for Removal from Protocol Therapy

- a. Progressive disease (See Section 13)
- b. Completion of course 24 of therapy
- c. <15% reduction in target tumor volume after course 8 of therapy
- d. <20% reduction in target tumor volume after course 12 of therapy
- e. Refusal of further protocol therapy by subject/parent/guardian
- f. Non-compliance that in the opinion of the investigator does not allow for ongoing participation.
- g. Physician determines it is not in the subject's best interest.
- h. Patient becomes pregnant
- i. Participant is prescribed a non-allowed concomitant medicine during study.
- j. Withdrawal of protocol consent
- k. Any surgical procedure on a target PN.
- l. PD-0325901-related toxicity requiring removal (see Section 8).

Subjects who are off protocol therapy are to be followed until they meet the criteria for Off Study (see below).

11.2 Off Study Criteria

For subjects who did not have a response (<20% shrinkage of target tumor) or have tumor progression ($\geq 20\%$) at any time:

- a) Thirty days after the last dose of PD-0325901 (but note that subjects with ongoing toxicity

should be followed until the toxicity resolves or 30 days, whichever is longer)

For subjects who had a response ($\geq 20\%$ target tumor shrinkage by 12 cycles) and never experience tumor progression:

- b) Completion of their one year follow-up MRI scan

For all subjects (supercedes "a" or "b"):

- c) Death
- d) Lost to follow-up
- e) Withdrawal of consent for any further data submission.
- f) Initiation of subsequent other medical treatment directed towards the plexiform neurofibroma
- g) Initiation of medical treatment (e.g. chemotherapy, biologic therapy, radiation therapy) directed towards other NF1-related tumor such as an optic pathway glioma

12.0 STATISTICAL AND ETHICAL CONSIDERATIONS

12.1 Subject Accrual

Subjects of both genders, from all racial and ethnic groups are eligible for this trial if they meet the criteria outlined in Section 4.0. To date, there is no information that suggests differences in drug metabolism or disease response among racial or ethnic groups or between the genders, indicating that results of the trial will be applicable to all groups. Efforts will be made to extend the accrual to a representative population, but in a phase II study with limited accrual, a balance must be struck between subject safety considerations and limitations on the number of individuals exposed to potentially toxic or ineffective treatments on the one hand, and the need to explore gender, racial, and ethnic aspects of clinical research on the other. If differences in outcome that correlate to gender, age, racial, or ethnic identity are noted, accrual may be expanded or additional studies may be performed to investigate those differences more fully.

12.2 Statistics and Feasibility

The primary objective of this study is to determine if there is an adequate level of disease responsiveness to PD-0325901 in adolescents and adults with NF1 and inoperable plexiform neurofibromas.

Sample Size

Minimum: 9 evaluable subjects Maximum: 19 evaluable subjects Target: 17 evaluable subjects. To allow for 10% unevaluable subjects, a maximum of 19 subjects will be enrolled. We anticipate enrollment to be completed in 24 months with primary outcome measure defined in 30 months.

The sample size for this trial is based on three primary factors: safety based on risk versus benefit; efficacy of 25% response rate and power of 80% to achieve feasibility if this rate were true. In order to balance these factors, we propose a two stage Simon Optimal Design³². Two stage designs are designed to provide an overall Type I error that is based on the probability of stopping at the end of Stage 1 plus the conditional probability of rejecting the drug given one passed Stage 1 to get to Stage 2. Thus, the overall Type I error was set at 5% and power at 80%. We assume a null hypothesis success rate of 5% versus a treatment with a 25% response rate.

Stage 1 will consist of 9 subjects to provide evidence of effectiveness and safety. If at least 1 of the 9 subjects achieves a radiographic response ($\geq 20\%$ reduction in tumor volume) the study will be allowed to recruit the total sample size of 17 evaluable subjects. The Stage I boundary is the same 0 of 9. The second stage of the design requires only 3 or more of the 17 subjects to have a positive response. If the null hypothesis is true, there is a 63% chance of terminating after Stage 1. If the probability of success is actually 0.25, there is a 92% chance that 1 or more subjects will exhibit a 20% reduction in tumor volume at Stage 1. Thus, it is expected that the trial will continue with continuous recruitment if the 25% success rate is correct.

For safety reasons, subjects who do not achieve at least a 15% reduction in tumor volume will not be continued beyond 8 cycles, as the likelihood of achieving a response (20% reduction in tumor volume) by 12 months is minimal. These subjects will be discontinued from the trial and counted in an "Intent to Treat" analysis as evaluable and as failures. If there are no subjects with a response (20% or more reduction in tumor volume) by the end of 8 cycles, but one or more with a 15% or more tumor volume reduction, recruitment will be suspended until the decision on futility (0 of 9 with at least 20% or more reduction in tumor volume after 12 cycles) or successful continuation can be definitively recommended. That is, if there are a number of subjects with 15% up to but not achieving a 20% reduction in tumor volume, the study will follow those subjects up to their post cycle 12 visit to determine if the recruitment can be restarted. If none of these 9 achieves a 20% tumor volume reduction by 1 year, the study will be terminated.

12.3 Statistical Analysis Plan

The basic statistical analysis plan for this proof of concept study will describe the subject population by baseline characteristics: clinical, PK/PD, Quality of Life and pain scores at baseline. Following complete accrual, study logistics will be summarized as per a Consort Diagram with reasons for withdrawal or unable to complete the study tabulated. Appropriate data analysis sets will be defined. The full-analysis set will include data from all subjects who receive ≥ 1 dose of therapy on this study; a safety analysis set will comprise data from subjects in the full-analysis set with any treatment doses. Other data sets (responding, evaluable, and pharmacodynamic/pharmacokinetic data sets) will be defined and will include data from subjects who have the necessary baseline and on-study measurements to provide interpretable results for specific parameters of interest.

Descriptive summaries will be prepared to show sample size, mean, standard deviation, 95% confidence intervals (CIs) on the mean, median, minimum, and maximum for continuous variables and counts, percentages, and 95% CIs on the percentage for categorical variables. For endpoints relating to tumor control, subject well-being, and biomarkers, analyses will be done based on the full-analysis, responding, evaluable, or pharmacodynamic data sets, as appropriate. Time-to-event analyses will be performed with reference to the date of first treatment on this study. Analyses will focus on evaluation of outcomes within each treatment arm and will be largely descriptive in nature as per the sample size justification section. Changes in tumor volumes, etc. will be summarized by medians, ranges, and the corresponding 95% CI. Continuous and categorical variables will also be summarized as appropriate.

Based on the safety analysis set, information regarding study treatment administration, drug dosing and course compliance, safety variables, will be described and summarized. Using data from the pharmacokinetic analysis set plasma concentrations will also be described and summarized. Peak, Trough, Area under the curve and mean serum levels will be compared to

tumor responsiveness. Safety will be assessed via tabulations of AEs and SAEs as well as Diary recordings following treatment dose/course of therapy.

All analyses for outcome results will be based on evaluable subjects, as defined in section 12.4.

At the end of the trial, we will report poor performance if the treatment is rejected at Stage 1, not meeting the criteria of at least 1 success in 9 cases. If there is no success at Stage II, we will report a failure to reject the null hypothesis using the conditional probability of the added subjects. If the null hypothesis is rejected, the probability of the estimated success rate will be reported and 95% confidence intervals as well as the distribution of changes in tumor size.

An early stopping rule will be invoked to potentially prevent accrual of subjects onto the study in the event that PD-0325901 is associated with a higher than acceptable rate of dose-limiting toxicity (DLT) requiring removal from study (set at 10% or higher) during the first 2 courses. Toxicity will be continuously monitored. As per the 2nd table below, if at any time >2 of the first 10 subjects or 4 or more of the first 15 total subjects are removed for toxicity as per Section 8.3, then accrual will be stopped until the DSMB reviews safety and efficacy data for the study and recommends termination or despite the DLT (because of the benefit:risk assessment or other reasoning) recommends reopening recruitment.

Table 1: Stopping Boundaries requiring DSMB to consider terminating trial

Number of subjects	Trial will be stopped if the number of subjects with severe toxicity is greater than or equal to the number below
10	3 (equivalent to a p-value of 0.07 that the rate of severe toxicity is 10% or less)
15	4 (equivalent to a p-value of 0.055 that the rate of severe toxicity is 10% or less)

Using these rules and the binomial distribution, the chance of putting the trial on hold and potentially stopping early within the first 10 subjects:

True probability of toxicity	Chance of stopping early
.10	7%
.20	32%
.25	47%
.30	62%
.35	74%
.40	83%

In addition, any episode of retinal vein occlusion will halt enrollment until the DSMB reviews the case and the study and recommends termination or despite the DLT recommends reopening recruitment.

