A Phase 1 trial of PD-0325901 was conducted in 66 patients with advanced cancer²⁷ to evaluate different doses and dosing schedules. They found that twice a day dosing sustained target suppression more completely than did once daily dosing. Common adverse events were rash, diarrhea, fatigue, nausea, and visual disturbances including retinal vein occlusion (RVO; n = 3). Acute neurotoxicity (visual disturbance, balance, and gait disorders) was common in patients receiving \geq 15 mg BID, regardless of schedule. The maximum tolerated dose, 15 mg BID continuously, was associated with late-onset RVO outside the dose-limiting toxicity window. An alternative dose and schedule, 10 mg BID 5 days on/2 days off, was therefore expanded; one RVO event occurred. In contrast to the neurotoxic effects observed, all episodes of RVO presented quite late, after 13, 15, and 36 weeks of therapy. A retrospective analysis of relevant visual episodes found predisposing factors for retinopathy (hypertension, diabetes, hypercholesterolemia, and glaucoma) in all patients with RVO but no correlation with cumulative PD-0325901 dose. No patients on a 3 week on/1 week off dosing regimen developed RVO. Finally, they determined that doses \geq 2 mg bid, which achieved the plasma levels consistent with target inhibition in xenograft mouse models, caused \geq 60% suppression of pERK signaling in melanoma tissue from patients.

An open-label, phase II study of PD-0325901 evaluated 15 mg bid given intermittently (3 weeks on/1 week off) to 13 patients with advanced non-small cell lung cancer²⁸. Of 13 patients treated, three discontinued due to adverse events (blurred vision, fatigue, and hallucinations, respectively). The study was then altered to 5 days on/2 days off for 3 weeks, followed by 1 week off and another 21 patients were enrolled. Main toxicities included diarrhea, fatigue, rash, vomiting, nausea, and reversible visual disturbances. There were no objective responses. Seven patients had stable disease. Neither phase I nor II PD-0325901 trials have been conducted in children.

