10.4 Reporting Procedures for All Adverse Events

All observed or volunteered adverse events, regardless of suspected causal relationship to study drug, will be recorded as Adverse Events in the case report forms and submitted to the Operations Center within 2 weeks of completion of each treatment course. Events involving adverse drug reactions, illnesses with onset during the study, or exacerbation of pre-existing illnesses should be recorded. Objective test findings (e.g., abnormal laboratory test results) should also be recorded.

It will be left to the investigator's clinical judgment whether or not an adverse event is of sufficient severity to require that the subject should be removed from treatment. A subject may also voluntarily withdraw from treatment due to what he or she perceives as an intolerable adverse event. If either of these occurs, the subject will be given appropriate care under medical supervision until symptoms cease or until the condition becomes stable.

Adverse events will be assessed by the treating investigator for relationship to the study drug (unrelated, unlikely, possible, probable, or definitely related).

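### Section 12.3 describes the event behind the toxicity pause in three ways, and its operative sentence omits subjects who have a qualifying toxicity and then stop by their own or the investigator's decision

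*Combined protocol and SAP*

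**What the plan says.** Section 12.3 describes the counted event in three ways.

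- **Purpose sentence:** dose-limiting toxicity "requiring removal from study (set at 10% or higher) during the first 2 courses".
- **Operative sentence:** a pause "if at any time >2 of the first 10 subjects" meet the criterion. The second limit, where the criterion is named, is "4 or more of the first 15 total subjects are removed for toxicity as per Section 8.3".
- **Boundary table heading:** "Trial will be stopped if the number of subjects with severe toxicity is greater than or equal to the number below". Severe is not defined. The entry for 10 subjects is 3, described as "equivalent to a p-value of 0.07 that the rate of severe toxicity is 10% or less".

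A second table gives the chance of a hold within the first 10 subjects for true toxicity probabilities from 10% to 40%.

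Section 8.3 requires removal in these cases:

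- an 8.1 or 8.2 toxicity recurs on the reduced dose;
- a Grade 3 or higher toxicity has not returned to Grade 1 or lower within 2 weeks;
- retinal vein occlusion, glaucoma, raised eye pressure or another significant eye finding develops.

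Section 10.4 adds two other routes out. One is the investigator's clinical judgment. The other is the subject's own decision: "A subject may also voluntarily withdraw from treatment due to what he or she perceives as an intolerable adverse event". Section 11.1 lists "Refusal of further protocol therapy by subject/parent/guardian" as item e, physician decision as g and withdrawal of consent as j. Drug-related toxicity requiring removal under Section 8 is a separate item, l. Nothing adds e, g or j to the pause count when the reason is drug toxicity.

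**The concern.** This is the trial's only numerical toxicity rule. A DSMB applying it needs to know which subjects to count, and 12.3 gives three answers that can differ for the same subject. Under the operative sentence, some subjects who have a qualifying drug toxicity and leave treatment add nothing to the count.

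Feasibility and toxicity are a secondary aim, and the tumours are benign. Some subjects could therefore reasonably decline to restart after a toxicity. If they do, accrual may continue at a rate of toxicity stops that the printed table suggests would usually cause a pause.

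**Working it through.** **1. Reproduce the plan's figures.** With independent subjects and event probability p, the chance of reaching the limit at 10 subjects is

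P(X ≥ 3) = 1 − Σ(x = 0 to 2) C(10, x) pˣ (1 − p)¹⁰⁻ˣ.

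At p = 0.30 this is 1 − (0.0282 + 0.1211 + 0.2335) = 0.617.

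| p | Computed | Printed in 12.3 |
|---|---|---|
| 0.10 | 7.0% | 7% |
| 0.20 | 32.2% | 32% |
| 0.25 | 47.4% | 47% |
| 0.30 | 61.7% | 62% |
| 0.35 | 73.8% | 74% |
| 0.40 | 83.3% | 83% |

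The tail probabilities at a 10% rate are 0.0702 for 3 of 10 (printed 0.07) and 0.0556 for 4 of 15 (printed 0.055). The arithmetic is sound. The question is what p refers to.

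**2. Apply the three descriptions to two subjects whom the protocol's rules allow.**

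| Subject | Met 8.1 or 8.2? | Met 8.3? | Counted by operative sentence? | Counted by table heading? |
|---|---|---|---|---|
| Related Grade 3 event that recovers within 2 weeks; subject declines to restart | Yes | No: recovered in time, no recurrence on a reduced dose | No | Probably, but severe is undefined |
| Related, clinically significant, non-ocular Grade 2 toxicity that never returns to Grade 1 | Yes | No: the 2-week item starts at Grade 3, and without a restart there can be no recurrence on a reduced dose | No | On an ordinary reading, no |

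The second subject shows a gap between sections. Section 8.2 (and 8.1 for blood counts) holds the drug until recovery to Grade 1 or lower, but 8.3 has no removal item for a Grade 2 toxicity that never gets there. Such a subject has to leave by another 11.1 route, such as e, g or j.

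**3. Effect on the chance of a pause.** Let T be the true rate of permanent stops following a related 8.1 or 8.2 toxicity, and c the share of those stops that meet 8.3. The rule sees p = cT. The documents do not give c, so it is an assumption, shown over a range for T = 30%:

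| c | p = c × 0.30 | Pause within first 10 | Pause at 10 or 15 |
|---|---|---|---|
| 1 | 0.30 | 62% | 75% |
| 2/3 | 0.20 | 32% | 42% |
| 1/2 | 0.15 | 18% | 24% |
| 1/3 | 0.10 | 7% | 9% |

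The last column adds the second limit: the chance of at least 3 in the first 10, or fewer than 3 there but at least 4 in the first 15. At c = 1/3, a true rate of 30% triggers a pause no more often than the 10% reference rate does under full counting.

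**4. Time window.** The purpose sentence limits events to the first two courses. The operative sentence has no such limit and says the check applies at any time. An 8.3 removal for recurrence after a dose reduction could fall after course 2, so the choice of window can change the count.

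**The case against.** Counting objective, protocol-defined removals is a legitimate choice, and the protocol never says that its stopping chances cover every toxicity-related exit. The table heading would probably catch the Grade 3 subject above. Section 11.1 is a list of removal criteria and does not say that its items are mutually exclusive. The phrase about any time may refer to when the count is checked rather than when the event occurs. All of this is fair, but it shows that the text can be read in more than one way. A pause rule should not depend on which sentence the DSMB reads.

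Other safeguards limit the consequence. Dose-limiting toxicities are notified at once (Section 8.0), events bearing on benefit and risk are expedited (10.5), and any retinal vein occlusion halts enrolment (12.3). The DSMB and medical monitor have general oversight (14.0). It would be wrong to say that the trial would be blind to such toxicity. None of these provisions changes the count, however.

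A broad remedy would strain the limits, which are tied to a 10% rate. If every stop to which toxicity merely contributed were counted, and an acceptable rate for that wider event were 15% or 20% (assumptions), the chance of a needless pause within 10 subjects would be 18% or 32%, against the stated 7%. That objection stands, and it is why the fix is confined to toxicities that already met 8.1 or 8.2.

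A reader might infer from the lung cancer study described in Section 2.2 that uncounted exits have already been seen on this schedule: of 13 subjects, "three discontinued due to adverse events (blurred vision, fatigue, and hallucinations, respectively". The documents do not support this. They do not say who decided or under what rule, and the dose was 15 mg bid against a maximum of 4 mg bid here. Nor can those three stops be sorted by whether they would have met 8.3. That section also covers recurrent Grade 2 toxicity and eye findings of any grade. Section 6.1.5 lists one Grade 3 hallucination, while its Table 2 lists two subjects with hallucination on that schedule.

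**Conclusion.** The point holds in a limited form. Section 12.3 gives three inconsistent descriptions of the counted event and leaves the window unclear. Under its operative sentence, a permanent stop after a related toxicity that met 8.1 or 8.2 is not counted when the subject leaves by choice or investigator judgment and no 8.3 criterion is met.

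The stopping-chance table is labelled only by the true probability of toxicity. Read as covering all such stops, it overstates the rule's sensitivity. How far depends on the unknown share meeting 8.3: step 3 of the working shows anything from no loss to a fall to the level of the 10% reference rate. The documents do not show that this share is low, and the printed probabilities are not miscalculated. This is a definition that should be repaired because the repair is cheap. It does not show that the safety monitoring has failed.

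**What to change.** - **One counted event.** Use the same definition in the 12.3 trigger sentence, the boundary table heading and the stopping-chance table: 8.3 removals, plus any permanent stop following an at-least-possibly-related toxicity that met 8.1 or 8.2, whatever 11.1 reason is recorded. Keep the limits of 3 of 10 and 4 of 15.
- **One window.** State whether events count in the first two courses only or throughout treatment.
- **One form item.** Record on the off-therapy form, if it does not already do so, whether such a toxicity was the main reason for stopping. This separates toxicity stops from later exits for other reasons, such as too little shrinkage after course 8. The form is not in the documents, so its present content is unknown.
- **Reconcile 8.1 and 8.2 with 8.3** for a Grade 2 toxicity that does not recover. How such a subject is managed is for the sponsor to settle. This change concerns only the trial-level count and leaves the patient-level rules in Section 8 as they are.

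The cost is a small edit to 12.3 and one data item. A DSMB pause becomes more likely, but it prompts a review and not automatic termination. The 7% chance at a 10% rate would then refer to the broader event, and the sponsor should confirm that 10% is still the intended reference rate for it.
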